## **9.            CRITERIA FOR PATIENT DISCONTINUATION**

Patients who meet the following criteria should be discontinued from the study:

- Disease progression, including disease transformation,
- Intercurrent illness that prevents further administration of treatment,
- Unacceptable adverse event(s),
- Patient decides to withdraw from the study, or
- General or specific changes in the patient's condition render the patient unacceptable for further treatment in the judgment of the investigator
- Incorrect enrollment of subject
- Stem-cell transplant
- Cases of potential drug-induced liver injury that include an elevated ALT or AST in combination with either an elevated bilirubin or clinical jaundice, as defined by Hy's law:
  - Treatment-emergent ALT or AST  $> 3 \times$  ULN in combination with total bilirubin  $> 2 \times$  ULN
  - Treatment-emergent ALT or AST  $> 3 \times$  ULN in combination with clinical jaundice

## **9.1 GENERAL CRITERIA FOR DISCONTINUATION**

- Inability of patient to comply with study requirements
- Determination by the investigator that it is no longer safe for the patient to continue therapy
- If there is evidence of a lack of efficacy associated with the experimental therapy or if there is sufficient evidence of efficacy to warrant phase II testing
- Medication may show serious adverse effects and trial may be stopped for unacceptable safety.
- Persistent abnormal laboratory results related to the trial medications.
- Rapid deterioration of patients secondary to primary neoplasia that would preclude the continuation of the systemic therapy.
- Patient preference to discontinue experimental treatment as well as poor compliance with protocol.

## **10. CLINICAL AND LABORATORY EVALUATIONS**

### **10.1 PRETREATMENT EVALUATIONS**

- Pregnancy test (serum or urine) for women of childbearing potential.
- Medical history and documentation of the rationale for treatment of the patient's disease with Venetoclax, ibrutinib and rituximab.
- Physical examination, including vital signs, blood pressure, performance status and tumor assessment.

Baseline laboratory evaluations such as :

- Hematology (within 2 weeks of treatment): complete blood count (CBC) with differential and platelet count.
- Serum Chemistries: glucose, BUN, creatinine, uric acid, total bilirubin, alkaline phosphatase, LDH, total protein, albumin, SGOT(AST), SGPT (ALT), and calcium.
- Baseline CT/PET, bone marrow evaluation

### **10.2 EVALUATIONS DURING TREATMENT**

Please refer to Study Flowchart, Appendix 1.

### **10.3 POST-TREATMENT EVALUATIONS**

Please refer to Study Flowchart, Appendix 1.

## **11. EVALUATION OF RESPONSE**

Preliminary efficacy of the combination of Ibrutinib, Venetoclax and Rituximab, objective tumor response rate (ORR) will be evaluated after 2, 4 and 6 cycles of 28 days after initiation of treatment and later every 3 cycles until disease progression, patient taken off study or study ends.

Radiological tumor assessments (+/- 14 days):

- Chest CT/MRI
- Abdomen and pelvis CT/MRI scan
- PET Scan evaluations Q2 cycles- based on investigator's criteria. If positive at baseline, will be repeated to confirm CR
- Response Evaluation using Cheson Criteria 2014

The outcomes will be correlated with progression-free survival and overall survival.

## **12. STATISTICAL CONSIDERATIONS**

The main aim of this Phase I study is determining maximum tolerated dose (MTD) among 2 doses of venetoclax once daily in combination with Ibrutinib/Rituximab. The secondary aim of the study is to evaluate efficacy, progression-free survival and overall survival of patients in the expansion cohort at the determined MTD.

### **Dose escalation part:**

#### **Study Endpoints**

The primary endpoints for this Phase I study are to determine the MTD, safety, and toxicity of the combination of venetoclax in combination with ibrutinib/rituximab. For this study, cohorts of 3-6 patients are used for each dose level. The dose level in which 2 patients experience unacceptable toxicity is usually considered the MAD. We will define the MTD as the next lower dose level in which no more than 1/6 patients experience unacceptable toxicity. Counts (percentages) of toxicity events will be reported.

#### **Sample Size/Accrual Rate**

The MTD will be determined in a standard fashion using 3-6 patients per dose level. No more than 2 dose levels will be used in order to find the MTD. As such, for the phase I escalation portion of the study, no more than 12 patients will be required. The Expansion cohort will be a maximum of 24 patients. Between the dose-escalation and dose-expansion, the maximum number of subjects will be 30.

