## **3. OVERALL STUDY DESIGN**

This is a Phase 1b, single-arm, open-label, single-center study of venetoclax (ABT-199) in combination with ibrutinib and rituximab in Subjects with Relapsed/Refractory DLBCL. The trial consists of a dose-escalation of venetoclax in combination with standard doses of ibrutinib and rituximab. For the dose escalation part of the study, a standard 3+3 design will be utilized. Once the MTD has been established, the dose escalation part will be followed by a dose expansion part in a cohort with a maximum of 24 subjects with DLBCL. The purpose of the dose expansion part is to investigate the efficacy of the combination. Between the dose-escalation and dose-expansion, the maximum number of subjects will be 30.

Cycle length will be 28 days. Venetoclax will be administered orally QD, continuously for 24 cycles (from C1D2). Ibrutinib will be administered orally QD, continuously for 24 cycles (from C1D2). Rituximab will be administered IV per institutional standards. weekly X 4 (Cycle 1); once on Day 1 of cycles 2-6 only, then every other cycle until Cycle 24 (total 18 doses of Rituxan from C1D1), Commercially available rituximab IV will be used.

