## 5. TREATMENT

The investigator will instruct the patient to take the study drugs as per protocol. All dosages prescribed and dispensed to the patient and any dose change or interruption must be recorded in the dosage administration record CRF, as appropriately.

This is an open-label dose escalation study using a 3+3 design. Before applying the dose escalation rules, 3 subjects in any given cohort must have completed the DLT observation period which is defined as 28 days (1 cycle) of therapy followed by evaluation for toxicity on Cycle 2 Day 1 (Study Day 29 +/- 3 days). The dose level in which 2 patients experience unacceptable toxicity is usually considered the maximum administered dose (MAD). We will define the MTD as the next lower dose level in which no more than 1/6 patients experience unacceptable toxicity. Dose escalation will cease if 2 or more patients develop DLT. There will be no intrapatient dose escalation.

Enrollment in a cohort will proceed as follows:

- If no dose limiting toxicity (DLT) is observed during the DLT observation period in the initial 3 subjects of a cohort, dose escalation to the next higher dose level cohort will occur.
- If 1 DLT is observed, 3 additional subjects will be enrolled at the same dose level for a total of at least 6 subjects. If no further DLT(s) are observed, escalation to the next higher dose level cohort will occur.

Dose escalation will occur at the planned dose levels until the MTD is determined or until the highest dose level is tested. The MTD is defined as the highest dose at which <33% of the subjects enrolled in a cohort experience a DLT. At least 6 subjects will be treated at the MTD or highest tested dose.

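### The limits of two dose levels and 12 patients for finding the MTD can fail on one uncommon path, because both dose tables include level −1 and the plan does not say when the six patients at the MTD are counted

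*Combined protocol and SAP*

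**What the plan says.** **Limits.** Section 12, Sample Size/Accrual Rate, says "No more than 2 dose levels will be used in order to find the MTD" and that "for the phase I escalation portion of the study, no more than 12 patients will be required". The sample size justification in Section 6 repeats both limits. The opening of Section 12 describes the aim as "determining maximum tolerated dose (MTD) among 2 doses of venetoclax once daily".

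**Dose levels.** The dose escalation schema in Section 3 and the table in Section 6 each list three levels, with venetoclax at 200 mg (level −1), 400 mg (level 1) and 800 mg (level 2). In the available text, the level −1 row has no patient count in Section 6, and in Section 3 it carries an asterisk whose note is not reproduced.

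**Escalation rules.** Section 3 says "a standard 3+3 design will be utilized". Under Section 5, 0/3 escalates and 1/3 leads to three more patients. For two or more DLTs the instruction is "Dose escalation will cease if 2 or more patients develop DLT".

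**MTD rules.** Section 5 contains three statements:
- "We will define the MTD as the next lower dose level in which no more than 1/6 patients experience unacceptable toxicity" (repeated in Section 12, Study Endpoints);
- a separate definition of the MTD as the highest dose at which under 33% of a cohort has a DLT;
- "At least 6 subjects will be treated at the MTD or highest tested dose".

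**Order.** Section 3: "Once the MTD has been established, the dose escalation part will be followed by a dose expansion part".

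**The concern.** Two levels of six patients give 12 only if a third level can never be used. Level 1 can be left with three patients after 0/3. If level 2 then fails, three patients cannot show a rate of at most one in six, so level 1 has to be filled to six. If that fill fails, the only lower level left is −1. On this path the team would hold two conflicting instructions: go down a level, as the MTD rule implies, or stop because two levels have been used. The MTD is the primary objective, so this should be settled before any DLT data exist.

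**Working it through.** **The plan's figure.** 2 levels × 6 patients = 12. It reproduces.

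**Paths under the Section 5 rules, with six patients at the MTD required before expansion**

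| Path | Levels used | Maximum patients |
|---|---|---|
| Level 1 passes, level 2 passes | 2 | 6 + 6 = 12 |
| Level 1 passes, level 2 fails, level 1 holds at six | 2 | 6 + 6 = 12 |
| Level 1 fails on first pass, level −1 opens | 2 | 6 + 6 = 12 |
| Level 1 clears at 0/3, level 2 fails, level 1 fill fails, level −1 opens | 3 | 6 + 6 + 6 = 18 |

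Only the last path breaks a limit. It takes 6 at level 1, 3 or 6 at level 2 and 3 or 6 at level −1. The total is 12 (both of those levels fail at three), 15 or 18. Replacements for non-evaluable patients come on top.

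**How often.** The documents give no DLT rates by dose, so the rates below are assumptions. Write p₋₁, p₁, p₂ for the rates, q = 1 − p, and b(p) = 3p²q + p³ for two or more DLTs in three patients.

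- Level 1 fails on first pass: F₁ = 1 − q₁³ − 3p₁q₁²·q₁³
- Level 2 fails: F₂ = 1 − q₂⁶ − 6p₂q₂⁵
- Fill of level 1 reached: R = q₁³·F₂
- Three levels used: T = R·b(p₁)
- P(N=18) = q₁³·b(p₁)·[F₂ − b(p₂)]·[1 − b(p₋₁)]
- P(three levels, N=12) = q₁³·b(p₁)·b(p₂)·b(p₋₁)
- P(N=15) = T minus the two lines above; P(N>12) = P(N=15) + P(N=18)

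Worked case, rates 10/20/30%:
- q₁³ = 0.512; F₂ = 1 − 0.1176 − 0.3025 = 0.5798; R = 0.512 × 0.5798 = 0.2969
- b(0.2) = 0.104; T = 0.2969 × 0.104 = 0.0309
- b(0.3) = 0.216; b(0.1) = 0.028
- P(N=18) = 0.512 × 0.104 × 0.3638 × 0.972 = 0.0188
- P(three levels, N=12) = 0.512 × 0.104 × 0.216 × 0.028 = 0.0003
- P(N=15) = 0.0117; P(N>12) = 0.0306

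| Assumed rates, levels −1/1/2 | 5/10/20% | 10/20/30% | 10/25/40% | 15/30/45% |
|---|---|---|---|---|
| Level 1 fails on first pass (limits hold) | 9.4% | 29.1% | 40.0% | 50.6% |
| Fill of level 1 reached | 25.1% | 29.7% | 32.4% | 28.7% |
| Fill fails, given reached | 2.8% | 10.4% | 15.6% | 21.6% |
| Three levels used | 0.7% | 3.1% | 5.1% | 6.2% |
| P(N=15) | 0.2% | 1.2% | 2.3% | 3.1% |
| P(N=18) | 0.5% | 1.9% | 2.7% | 2.9% |
| **P(N>12)** | **0.7%** | **3.1%** | **5.0%** | **6.0%** |

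First-pass failure of level 1 makes up F₁/(F₁ + T) = 89–93% of the cases that need level −1.

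**Upper bound.** Since F₂ ≤ 1, T cannot exceed q₁³·b(p₁). This is largest near p₁ = 0.36: 0.2621 × 0.2955 = 0.0775. A grid over all rates that do not fall with dose gives the same maximum for P(N>12), and at most 3.2% for P(N=18).

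**The other reading.** If the six at the MTD may be completed in expansion, there is no fill within escalation. The maximum is then 12 and three levels are never used.

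**Where the two MTD definitions differ.** At six patients they agree: 1/6 = 16.7% passes both and 2/6 = 33.3% fails both. At three patients they do not: 0/3 is under 33%, but it is not a result in six.

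**The case against.** The strongest reply is that the plan never intended a fill within escalation. Section 5 also defines the MTD as under 33% of a cohort, and level 1 at 0/3 meets that with three patients. The MTD is then established, expansion opens in the order Section 3 requires, and the six are reached there. The layout fits this: the Section 6 table plans three patients at each of levels 1 and 2, Section 1.5.1 describes two dose cohorts accrued three at a time, and 3 + 3 + 24 = 30 is the overall cap. Section 5's enrollment steps contain no fill, and its sentence on six patients gives no timing. This stands as a tenable reading. It does not remove the point, because the rule of at most one in six appears in both Sections 5 and 12 and the text never says which definition governs.

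The two-level limit could also be read as a rule that ends the search. The documents do not say so, and it would leave level −1 unused although both tables list it.

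A reader might go further and infer four things that the documents do not support:
- That any use of level −1 breaks the limits. If level 1 fails on first pass, only levels 1 and −1 are used and 12 holds.
- That there is no de-escalation rule at all. The standard 3+3 design, the move to the next level down with at most one in six, and cohorts of three to six imply one. It is simply not written out.
- That patients are exposed to a higher dose. Nothing in the wording does this.
- That the overall cap of 30 is threatened. It is not.

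**Conclusion.** A minor inconsistency, held with medium confidence. The two-level and 12-patient limits do not fit dose tables with three levels if six evaluable patients with at most one DLT are needed before expansion. On that reading the true escalation maximum is 18. The chance of exceeding 12 is 0.7–6.0% in the four assumed scenarios and just under 8% at most. If the under-33% definition governs and the six may come from expansion, 12 is correct. Confidence is limited by the competing definitions and by the missing note to the asterisk on the level −1 row. It remains worth correcting because it concerns the algorithm for the primary objective.

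**What to change.** In Section 5, state that:
- the rule of at most one DLT in six governs the MTD, and the under-33% definition is aligned with it;
- six DLT-evaluable patients are required at the MTD before expansion opens;
- two or more DLTs at level 1, on first pass or after filling to six, open level −1 with three to six patients;
- level −1 is the MTD if at most one of six has a DLT; otherwise no MTD is declared.

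In the sample size text of Sections 6 and 12, restate the limits as up to three dose levels (−1, 1, 2) and at most 18 DLT-evaluable patients, with the overall cap of 30 unchanged. Bring the aim at the start of Section 12 into line.

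The cost is amendment wording, with no new procedures. The stated escalation maximum becomes less favourable (18 instead of 12). On the 18-patient path, 30 − 18 = 12 expansion places remain; on the 15-patient path, 15 remain.

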## Study Design

Description: A dose-escalation will first determine the MTD and/or RPII of Bruton's Tyrosine Kinase (BTK) Inhibitor, Ibrutinib (PCI-32765) plus venetoclax and rituximab in relapsed or refractory DLBCL / Dose level and escalation described below

No of Pts	Dose Level	Ibrutinib a mg PO daily	Venetoclax b mg PO daily	Rituximab c mg/m  IV Day 1
	-1	560	200	375
3	1	560	400	375
3	2	560	800	375

a. Ibrutinib will be administered orally daily beginning Cycle 1 Day 2 for 24 cycles

b. Venetoclax is being administered orally daily, continuously beginning Cycle 1 Day 2 for 24 cycles

c. Rituximab will be administered IV per institutional standards; weekly X 4 (Cycle 1); once on Day 1 of cycles 2-6 only, then every other cycle until Cycle 24 (total 18 doses of Rituxan from C1D1)

Total number of patients: 30

Total Number of Centers: One center

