## Sample Size

Justification: The MTD will be determined in a standard fashion using 3–6 patients per dose level. No more than 2 dose levels will be used in order to find the MTD. As such, for the phase I escalation portion of the study, no more than 12 patients will be required. Also we plan an expansion cohort at the MTD to examine the efficacy of the combination. We plan an expansion cohort with a maximum of 24 patients. Between the dose-escalation and dose-expansion, the maximum number of subjects will be 30.

Subjects with relapsed / refractory DLBCL that decide to participate on this study will sign consent and enter a screening period of 28 days. Patients that fulfill and maintain eligibility criteria will start cycle 1 day 1 treatment by receiving *Rituximab*. *Ibrutinib and venetoclax* will be administered daily starting on cycle 1 day 2. Follow up will be weekly during Cycle 1, on days 1 and 15 of cycles 2 and 3, then follow up monthly until disease progression, unacceptable toxicity or withdraw of consent.

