#### **MTD and Expansion Cohort Analysis**

The efficacy endpoint is progression-free survival (PFS) and overall survival (OS) of the patients enrolled in the expansion cohort and those treated at the MTD dose.

The duration of PFS is defined as the time from the beginning of the first cycle of treatment to the date of progressive disease or death from any cause whichever occurs first.

The duration of OS is defined as the time from the beginning of the first cycle of treatment to the date of death from any cause.

Both time-to-event variables, PFS and OS, will be estimated by the Kaplan-Meier method, estimates of survival in reported at 6, 12, 18, 24, 30 and 36 months and the corresponding 95% confidence intervals will be reported.

Toxicity rate in the expansion cohort will be evaluated and summarized using frequency and a corresponding exact binomial 95% confidence interval.

All subjects treated with an investigational product will be included in the analysis.

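### The cap of 30 can leave fewer than the 24 expansion patients for which the toxicity rule's 80% power is computed, and the plan does not say whether escalation patients at the MTD count

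*Combined protocol and SAP*

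**What the plan says.** Three maxima are set.

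- Escalation: with 3 to 6 patients per level and at most two levels, "no more than 12 patients will be required" (Section 12, Sample Size/Accrual Rate).
- Expansion: "We plan an expansion cohort with a maximum of 24 patients" (Section 6, Sample Size). Section 3 says the same: "the dose escalation part will be followed by a dose expansion part in a cohort with a maximum of 24 subjects with DLBCL".
- Overall: 30, in Sections 3, 6 and 12. Section 12, Sample Size/Accrual Rate, sets it directly beside the expansion maximum: "The Expansion cohort will be a maximum of 24 patients. Between the dose-escalation and dose-expansion, the maximum number of subjects will be 30". The Study Design table in Section 6 repeats it: "Total number of patients: 30".

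Section 5 governs how many patients escalation uses: "If 1 DLT is observed, 3 additional subjects will be enrolled at the same dose level for a total of at least 6 subjects". It adds: "At least 6 subjects will be treated at the MTD or highest tested dose".

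The Stopping Guidelines in Section 12 derive a four-look toxicity boundary for an expansion cohort of 24. Inputs are 10% acceptable toxicity, 30% unacceptable toxicity, alpha 10% and power 80%. Table 1 stops at 3 of 5, 4 of 11, 5 of 17 or 6 of 24. Table 2 is headed as applying to n=24. Its high-boundary columns give a crossing probability of 0.047 at 10% toxicity and 0.800 at 30%. The text below it claims at least 80% and closes by referring to a sample of 24.

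On pooling, the MTD and Expansion Cohort Analysis takes PFS and OS in "patients enrolled in the expansion cohort and those treated at the MTD dose", but its toxicity sentence names the expansion cohort only. The DLT Definitions provide for replacing some escalation subjects without saying whether a replaced subject uses one of the 30 places.

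**The concern.** The three maxima add to 12 + 24 = 36 against a cap of 30, so they cannot all be reached with separate patients. Escalation and expansion must then either share patients or expansion must shrink, and the plan does not say which. The toxicity rule depends on the answer. Table 2 is its only quantified justification, and its power at 24 has no slack. If expansion is smaller, the rule misses a toxicity rate the plan calls unacceptable more often than the stated 20%. If patients are shared, some of the 24 have already been screened by the 3+3 rule, which Table 2 does not model.

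**Working it through.** **1. Reproduce Table 2.** Inputs are Table 1's looks (5, 11, 17, 24) and thresholds (3, 4, 5, 6). Carry the binomial distribution of the toxicity count from look to look, removing at each look the probability at or above the threshold. The probabilities of first crossing at the four looks are:

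| True rate | 5 | 11 | 17 | 24 | Total |
|---|---|---|---|---|---|
| 10% | 0.0086 | 0.0143 | 0.0115 | 0.0123 | 0.0467 |
| 30% | 0.1631 | 0.2829 | 0.1977 | 0.1559 | 0.7996 |

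The totals match the high boundary (0.047 and 0.800). Table 2's stopping probability of 0.770 and expected size of 14.6 reproduce only if the boundary is checked after every patient. With the four looks alone they are 0.644 and 15.8. Both bases are therefore shown below.

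**2. Expansion size if MTD escalation patients do not count.** Size = min(24, 30 − escalation): 24 after 6, 21 after 9, 18 after 12. Routes that use exactly six are:
- 0/3 at level 1, then 0/3 or at least 2/3 at level 2;
- at least 2/3 at level 1, then 0/3 at level −1.

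These leave 24 only if expansion patients supply the six-at-MTD minimum and no replaced subject takes a place under the cap. If every top-up to six is counted as escalation, a two-level escalation takes at least 3 + 6 = 9 and 24 is never reached.

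**3. Power of the printed rule at 30% toxicity.**
- N=21, printed looks: the look at 24 is not reached, so 0.1631 + 0.2829 + 0.1977 = 0.644.
- N=21, every patient, threshold 6 after patient 17: 0.644 + 0.065 = 0.709.
- N=18: a patient not stopped at 17 patients has at most 4 events in the cohort, so at most 5 at 18, and 6 is out of reach. Power is 0.644 on either basis. It reaches 80% only at a true rate of about 35.5%.

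**4. How often escalation exceeds six.** The documents give no DLT rates, so three pairs are assumed. Let a = P(0/3 at level 1), b = P(1/3, then 0/3 at level 1), o = P(1/3 at level 2). Given that level 1 is passed, and with expansion filling the six-at-MTD minimum:
- P(6) = a(1 − o)/(a + b)
- P(9) = [a·o + b(1 − o)]/(a + b)
- P(12) = b·o/(a + b)

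For 10%/10%: a = 0.729, b = 0.243 × 0.729 = 0.177, o = 0.243, so P(6) = 0.729 × 0.757/0.906 = 0.609.

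| DLT rates, levels 1/2 | P(6) | P(9) | P(12) | P(>6) |
|---|---|---|---|---|
| 10%/10% | 0.609 | 0.343 | 0.048 | 0.39 |
| 10%/30% | 0.450 | 0.464 | 0.086 | 0.55 |
| 30%/30% | 0.388 | 0.477 | 0.135 | 0.61 |

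These are conditional on an MTD at level 1 or 2. At 30%/30% only 0.494 of trials meet that condition.

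**5. If MTD escalation patients do count.** Then 12 + 18 = 30 gives 18 + 6 = 24 at the MTD. Those six had at most one DLT. Suppose the monitored event is the cycle-1 DLT at a 30% rate. P(0 of 6) = 0.1176 and P(1 of 6) = 0.3025, so the conditional weights are 0.28 and 0.72. The look at 5 cannot trigger. Continuing to 11, 17 and 24 gives 0.126 + 0.255 + 0.250 = 0.631.

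**The case against.** The strongest reply is that nothing is miscalculated. Maxima need not be reached together. Two natural readings give both 24 and 30: 6 + 24, matching the three-plus-three layout of the dose table, and 12 + 24 − 6 with six MTD patients shared. The 80% is also labelled for 24, in the Table 2 title and in the closing sentence. All of this stands. A reader might infer that Table 2 is wrong, or that the plan claims 80% at any sample size. The documents support neither: the high boundary reproduces, and the claim is tied to n=24. A reader might also infer that 80% cannot be had below 24. That holds only for the printed thresholds; step 3 does not rule out a re-derived boundary.

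The worst case should not be overweighted either. An escalation of 12 has probability 5% to 14% in step 4.

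Escalation itself also protects. If the monitored event were the cycle-1 DLT at 30%, level 1 would pass with probability 0.494. Detection by escalation or expansion together would then be 1 − 0.494 × (1 − 0.644) = 0.82 at N=18 and 0.82 to 0.86 at N=21, against 0.90 at N=24. But Table 2 takes no such credit, and the plan's reference to cumulative related toxicity does not establish that the two events are the same. The four-monthly DSMC review has no stated detection rate.

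What survives is that neither reconciling reading is stated for toxicity, and no figures are given for the sizes the cap can force.

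**Conclusion.** The point holds as an internal-consistency matter that affects a stated power, and it should be fixed. If MTD escalation patients are excluded, any escalation above six puts 24 out of reach. The chance of missing 30% toxicity then rises from 20% to between 29% and 36% at N=21, and to 36% at N=18. The 39% to 61% frequency rests on assumed DLT rates, an MTD at level 1 or 2, and the convention that expansion fills the six-at-MTD minimum. If MTD patients are included, the sample size is restored but Table 2's operating characteristics are not. The 0.631 applies only if the monitored event is the cycle-1 DLT.

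**What to change.** State whether escalation patients treated at the MTD, and replaced subjects, count toward the 30, the 24 and the monitoring looks.

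If MTD patients do not count, do one of the following.

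- Add the printed rule's power at the attainable sizes: 0.64 to 0.71 at 21 and 0.64 at 18.
- Tabulate matching boundaries. The expansion size is known when escalation ends, so the table can be fixed before the first expansion patient. Examples, by the same recursion:

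| N | Boundary | Alpha | Power |
|---|---|---|---|
| 21 | 3/5, 4/11, 5/17, 5/21 | 0.061 | 0.810 |
| 18 | 3/5, 4/11, 5/18 | 0.039 | 0.691 |
| 18 | 3/5, 4/11, 4/17, with no threshold of 4 at patient 18 | 0.085 | 0.800 |

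In the last row, also applying 4 at patient 18 raises alpha to 0.1003, above the plan's 10%. The higher false-stop rate against the higher power is the sponsor's choice.

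If MTD patients do count, define the monitored toxicity and recompute Table 2 conditional on passing escalation.

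The cost is one or two sentences and, if chosen, a short table.
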